9.1 TREATMENT/INTERVENTION PLAN

9.2 Concomitant Medications

The following medications are considered exclusionary during the study.

1. Any investigational anticancer therapy.
2. Any concurrent chemotherapy, radiotherapy (except palliative radiotherapy), immunotherapy, biologic or hormonal therapy for cancer treatment, other than TSH suppressive therapy and/or bisphosphonates and/or denosumab.
3. Immunosuppressive medications including, but not limited to, systemic corticosteroids at doses exceeding 10 mg/day of prednisone or equivalent, methotrexate, azathioprine, and TNF- α blockers. Use of immunosuppressive medications for the management of investigational product-related AEs or in subjects with contrast allergies is acceptable. In addition, use of inhaled and intranasal corticosteroids is permitted. A temporary period of steroids will be allowed for different indications, at the discretion of the principal investigator (e.g., chronic obstructive pulmonary disease, radiation, nausea, etc).
4. Live attenuated vaccines within 30 days of durvalumab dosing (i.e., 30 days prior to the first dose, during treatment with durvalumab and for 30 days post discontinuation of durvalumab). Inactivated vaccines, such as the injectable influenza vaccine, are permitted.

Contraception

Females of childbearing potential who are sexually active with a nonsterilised male partner must use at least 1 highly effective method of contraception (Table 1) from the time of screening, and must agree to continue using such precautions at least 90 days following the last infusion of durvalumab and avoid pregnancy for 9 months after RAI (¹³¹I) administration; cessation of birth control after this point should be discussed with a responsible physician. Periodic abstinence, the rhythm method, and the withdrawal method are not acceptable methods of birth control.

1. Females of childbearing potential are defined as those who are not surgically sterile (i.e., bilateral tubal ligation, bilateral oophorectomy, or complete hysterectomy) or postmenopausal (defined as 12 months with no menses without an alternative medical cause).
2. Subjects must use 2 acceptable methods of effective contraception as described in Table 1.

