3. Nonsterilised males who are sexually active with a female partner of childbearing potential must use 2 acceptable methods of effective contraception (see Table 1) from Day 1 and for 90 days after receipt of the final dose of investigational product. Males should avoid impregnating females partners for 9 months after RAI (¹³¹I).

Table 1: Highly Effective^a Methods of Contraception

Barrier/Intrauterine Methods	Hormonal Methods

• Male condom plus spermicide• Copper T intrauterine device• Levonorgesterel-releasing intrauterine system (eg, Mirena[®])^b	
• Etonogestrel implants: e.g. Implanon or Norplan• Intravaginal device: e.g. ethinylestradiol and etonogestrel• Medroxyprogesterone injection: e.g. Depo-Provera• Normal and low dose combined oral contraceptive pill• Norelgestromin/ethinylestradiol transdermal system• Cerazette (desogestrel)

^a Highly effective (i.e. failure rate of <1% per year)

^b This is also considered a hormonal method

Blood donation

Subjects should not donate blood while participating in this study for at least 90 days following the last infusion of durvalumab and a minimum 12 months after administration of RAI.

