- h: Patients should start a low iodine diet for 5 days prior to the first Thyrogen injection, and maintain the diet through 1 day after RAI is given.
- i: 0.9 mg Thyrogen will be administered intramuscularly in 2 consecutive calendar days. RAI is administered the calendar day after the second Thyrogen injection. Performance of a post-RAI whole body scan will be done as per standard of care per investigator discretion. The administration of these agents and evaluations will be performed in clinic. **If modification of durvalumab dose is required prior to RAI therapy, a delay in the schedule of Thyrogen and RAI administration is allowed as long as it is given prior to the second durvalumab dose.**
- j: These laboratory tests preferably will be performed prior to the first Thyrogen injection (not required).
- k: Serum or urine beta-hcg (for women of childbearing potential) is to be completed within 2 days prior to administration of RAI.
- l: Off-study evaluation will be performed within 30 days of the patient's last dose of durvalumab.
- m: The research blood sample can be obtained any time (for germline DNA).
- n: Radiologic guidance (CT, MRI or ultrasound guided) approaches and obtaining multiple cores to ensure sufficient biopsy material (at least 3 cores preferred) are allowed as long as it is considered safe for the patient (image-guided biopsies will be performed by a radiology physician with the appropriate expertise). The first research biopsy will be performed any time prior to Week 1 Day 1; the second research biopsy will preferably be conducted during Cycle 2, Week 3 or 4 (though alternate timing during Cycle 2 or later is allowed per investigator discretion or for safety reasons related to RAI administration).

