- o: Peripheral blood samples will be collected for peripheral T cell analysis as well as cfDNA analysis. For peripheral T cells, blood will be collected in 4 CPT tubes (BD, 8-ml capacity, total blood volume collected~32 ml for PBMC purification for flow cytometric analysis) and 1 PAXgene tube (BD order #762165 or equivalent) (for purification of RNA/DNA for TCR analysis). For cfDNA analysis, blood will be collected in 10-ml Cell-Free DNA BCT tubes (STRECK). These blood samples (peripheral T cells and cfDNA) will be collected Cycle 1/Week 1 (prior to durvalumab). In Cycle 1/Week 3 or 4, only the cfDNA sample will be drawn at various time points: on the day of first Thyrogen injection (but prior to Thyrogen injection) and on the day of RAI administration (but prior to RAI ingestion).
- p: Research blood collection (for peripheral T cell analysis and cfDNA analysis) after Cycle 1 will be conducted on Week 1 of Cycles 2, 3, and 4 (preferably prior to durvalumab administration, if possible), as well as Off Study. Cycle 2 cfDNA collection does not have to be performed if the Principle Investigator decides that it is redundant given the cfDNA collections performed for **footnote o**.
- q: Confirm availability of archival tumor tissue (if tissue is not already available at MSK, physical receipt of tissue is not required for study enrollment or initiation).
- r: TSH, thyroglobulin (TG), and antibody serologies for TG, thyroperoxidase (TPO), and TSH receptor (TSHR) will be drawn Cycle 1/Week 1 (prior to durvalumab). In Cycle 1/Week 3, TSH and TG will be drawn at various time points: on the day of first Thyrogen injection (but prior to Thyrogen injection) and on the day of RAI administration (but prior to RAI ingestion). Subsequently, TSH and TG will be drawn on Week 1 of every cycle. Additionally, antibody serologies for TG, TPO, TSHR will be required to be drawn on Week 1 of every even numbered cycle, up to and including Cycle 6.
- s: EKG will be performed in triplicate. Repeat the EKG in Cycle 1 (Week 3)(only 1 EKG required at that time point).
- t: If Cycle 1 Week 1 labs fall below screening requirements, the patient can start treatment at the discretion of the treating investigator if safety is not compromised.
- u: Week 1 evaluations/tests and research collections during Cycles 2 and beyond may be performed up to 3 days prior to the patient being treated.

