14.0 BIOSTATISTICS

The primary objective of this pilot study will be to assess the safety of administering durvalumab in combination with Thyrogen-stimulated RAI therapy in patients with recurrent/metastatic thyroid cancer. The period of dose limiting toxicity (DLT) monitoring will be 6 weeks beginning from the first durvalumab dose. Definitions for DLT are in Section 9.3. Subjects who are removed from the study for reasons other than DLT prior to the administration of the first Thyrogen injection will be replaced with another subject. Patients who do not complete the 6 week period of monitoring beginning from the first durvalumab dose for reasons other than DLT will also be replaced. If >1 of the first 3 patients, or >2 of the first 6 patients, develop DLT related to durvalumab, further accrual to the study will be halted. If this rule is not met, we plan to accrue 11 patients in total to this pilot study (see table below). All toxicities will be graded according to CTCAE v4.0.

Number of DLTs to stop in first 3 patients	Number of DLTs to stop in first 6 patients	Number of DLTs to stop in all 11 patients	Acceptable toxicity rate (H0)	Unacceptable toxicity rate (H1)	Type I error rate	Power
>1	>2	>2	0.10	0.35	0.101184466	0.80748277

Secondary objectives will be determining the best overall response rate (BOR; CRs plus PRs per RECIST v1.1 criteria) and progression-free survival (estimated using Kaplan-Meier methodology with time origin at the start of the treatment; PFS). For PFS, patients will be followed until progression of disease or death, whichever come first. Patients who continue treatment beyond initial investigator-assessed, RECIST 1.1-defined progression, and are subsequently removed from study within the

next radiographic assessment for progression, will be considered to have investigator-assessed progressive disease at the time of the initial progression event.

Exploratory objectives:

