Male patients should refrain from fathering a child or donating sperm during the study and for 90 days after the last dose of durvalumab monotherapy.

Pregnancy of the patient's partner is not considered to be an AE. However, the outcome of all pregnancies (spontaneous miscarriage, elective termination, ectopic pregnancy, normal birth, or congenital abnormality) occurring from the date of the first dose until 90 days after the last dose should, if possible, be followed up and documented.

Where a report of pregnancy is received, prior to obtaining information about the pregnancy, the Investigator must obtain the consent of the patient's partner. Therefore, the local study team should adopt the generic ICF template in line with local procedures and submit it to the relevant Ethics Committees (ECs)/Institutional Review Boards (IRBs) prior to use.

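### The sperm-donation and partner-pregnancy limits for men have no radioiodine term, so both can lapse before the plan's own 9-month post-radioiodine period ends

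*Combined protocol and SAP*

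**What the plan says.** **Men.** Section 17.2.2, Paternal exposure, sets one limit for both fathering and sperm donation: "Male patients should refrain from fathering a child or donating sperm during the study and for 90 days after the last dose of durvalumab monotherapy". It then says that the outcome of pregnancies in partners "occurring from the date of the first dose until 90 days after the last dose should, if possible, be followed up and documented". Section 9.2 (Contraception, item 3) has men use two methods from Day 1 until 90 days after the final dose, and adds: "Males should avoid impregnating females partners for 9 months after RAI". The blood-donation rule in Section 9.2 also has its own RAI term, a minimum of 12 months.

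**How long a man stays on study.** Section 13.1 removes patients for progression or unacceptable toxicity. Section 14.0 states: "For PFS, patients will be followed until progression of disease or death, whichever come first". Footnote l in Section 10.1 says: "Off-study evaluation will be performed within 30 days of" the last durvalumab dose.

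**Women.** Section 6.2 counts natural menopause only from age 60 with at least a year without menses. Unless surgically sterile, any other woman needs a negative serum test at entry. Section 9.2 defines childbearing potential for contraception and treats 12 months without menses as postmenopausal at any age. The test within 2 days before RAI (Section 5.3; Section 10.1, footnote k) is for women of childbearing potential. Neither place says which definition applies.

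**The concern.** Every patient is meant to receive about 100 mCi of I-131, yet the male limits in Section 17.2.2 are worded as if durvalumab were given alone. The plan carries an RAI term for conception and for blood donation, but none for sperm donation or for partner-pregnancy follow-up. A man who stops durvalumab early could donate sperm within the protocol's rules while still inside the period in which the same protocol tells him not to conceive. A partner pregnancy conceived in those months, against the 9-month rule, would fall outside the follow-up window.

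The secondary point is of the same kind. Section 5.3 treats pregnancy as a contraindication to RAI, but the definition that would decide who is retested just before it is looser than the one that decides who is tested at entry.

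**Working it through.** The plan gives no figure on this point, so the check is a comparison of texts and a calendar.

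**Inputs and assumptions**
- Durvalumab every 4 weeks (Section 4.3), so dose k falls on Day 1 + 28(k − 1).
- Earliest RAI: Thyrogen on the first two days of Week 3 (Days 15 and 16), RAI on Day 17.
- Latest on-schedule RAI: Day 28, the day before an on-time second dose. Footnote i says "a delay in the schedule of Thyrogen and RAI administration is allowed as long as it is given prior to the second durvalumab dose", and footnote o allows for Week 4: "In Cycle 1/Week 3 or 4, only the cfDNA sample will be drawn at various time points".
- 9 months = 274 days (assumed; 273–276 tested below).
- The man leaves the study at his last dose, so the phrase on study duration adds nothing. The results are therefore upper limits for the sperm-donation rule.

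**Formula.** Gap = (RAI day + 274) − (day of last dose + 90). The 9-month period ends on Day 17 + 274 = 291 to Day 28 + 274 = 302.

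| Last dose received | Day | 90-day window ends | Gap, RAI Day 17 | Gap, RAI Day 28 |
|---|---|---|---|---|
| 1st | 1 | 91 | 200 | 211 |
| 2nd | 29 | 119 | 172 | 183 |
| 4th | 85 | 175 | 116 | 127 |
| 6th | 141 | 231 | 60 | 71 |
| 8th | 197 | 287 | 4 | 15 |
| 9th | 225 | 315 | none | none |

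**Sensitivity**
- With 9 months = 273–276 days, the period ends between Day 17 + 273 = 290 and Day 28 + 276 = 304. The gap is then 199–213 days after one dose and 3–17 after eight. There is still none after nine (304 < 315).
- If the last dose in the follow-up rule is read to include RAI, a man with one durvalumab dose has a gap of 274 − 90 = 184 days (183–186).
- RAI may be delayed past Day 28. As an illustration, RAI on Day 42 with no second dose gives 42 + 274 − 91 = 225 days, so 211 is not a maximum.
- The ninth-dose crossover survives such delays. RAI must precede dose 2, and dose 9 falls at least 7 × 28 = 196 days after dose 2. The window then ends at least 196 + 90 = 286 days after dose 2, which is later than 9 months after RAI.

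**Which row is typical of an early stop.** The first scheduled scan is at 8 weeks ± 1 week. Removal for progression at that scan would normally follow at least two doses, so 172–183 days is a better guide than the one-dose row.

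**Women: interval between tests.** Take a woman under 60 with at least 12 months of amenorrhoea, no alternative cause and no sterilisation. She is tested at entry under Section 6.2. Under the Section 9.2 definition she is not of childbearing potential, so footnote k does not reach her. If her entry test is on Day 1, it is 17 − 1 = 16 to 28 − 1 = 27 days old at RAI; if 7 days earlier, 23 to 34. The 7-day window in footnote c is itself tied to childbearing potential. Under the general 4-week window of footnote f, the on-schedule maximum is 27 + 28 = 55 days. For women covered by footnote k the corresponding maximum is 2 days.

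**The case against.** The strongest reply is that the operative contraception rule sits in Section 9.2 and already contains the 9 months. Section 17.2.2 is a reporting section, and the two limits add to each other. That stands for conception. A reader might infer that men are cleared to father a child 90 days after durvalumab; the documents do not support this, because the Section 9.2 rule is not shortened by Section 17.2.2. It does not answer sperm donation, which Section 9.2 does not mention. Consent pages were not available and may say more, but they would not alter the protocol's own wording.

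Second, the Section 17.2.2 limit also runs for the duration of the study, so a man still followed for PFS may be covered for longer. That is true but not guaranteed: progression ends PFS follow-up and, with toxicity, is a ground for removal. The phrase does not apply to the partner-pregnancy window, which is in any case best-effort only.

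Third, a reader might infer that women in general go untested before RAI. They do not. Every woman of childbearing potential under Section 9.2 is retested within 2 days. The open group is narrow, already has a negative entry test and has a low pregnancy risk. It is missed only if a site applies the Section 9.2 definition.

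Finally, Section 9.2 says that women "must use at least 1 highly effective method of contraception (Table 1) from the time of screening", and a later item in the same list asks subjects for two methods. A reader might call this a contradiction. It is an ambiguity to tidy: a woman using two methods satisfies both sentences.

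**Conclusion.** The point holds in a limited form. The only sperm-donation limit in the available text, and the best-effort partner-pregnancy window, both lack an RAI term and can end before the plan's own 9-month period. For a man who leaves the study, the on-schedule shortfall is about 172–183 days after two doses, falling to 4–15 days after eight and to nothing from the ninth. One dose gives 200–211 days, and more if RAI is delayed. These figures rest on 28-day spacing and 274 days for 9 months. They measure a gap in the donation limit and in documentation, not in the conception rule.

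The pre-RAI test is a secondary point that depends on which definition a site applies. The documents give no age or sex mix, so the number of women affected among 11 patients cannot be estimated.

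Severity is minor. This is a cheap improvement to participant safety wording; the DLT stopping rule, sample size and analyses do not depend on it.

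**What to change.** 1. In Section 17.2.2, Paternal exposure, keep the study-duration clause and extend the sperm-donation limit to the later of 90 days after the last durvalumab dose and 9 months after RAI. Apply the same later-of end point to partner-pregnancy follow-up and, for consistency, to the fathering limit.
2. In Section 5.3 and footnote k of Section 10.1, require the hCG test within 2 days before RAI for every woman who needed the entry test under Section 6.2. Leave the Section 9.2 definition in place for contraception, so that no woman under 60 with long amenorrhoea is newly required to use it. Section 8.1 and footnote c need no change, because Section 6.2 already governs entry.
3. While amending, state one minimum number of methods for women in Section 9.2.

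The cost is a wording amendment and a few hCG tests. Men who stop early would have a longer donation limit and longer best-effort follow-up: up to 211 more days on schedule after one dose, longer if RAI is late, and none from the ninth dose.

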18.1 INFORMED CONSENT PROCEDURES

Before protocol-specified procedures are carried out, consenting professionals will explain full details of the protocol and study procedures as well as the risks involved to participants prior to their inclusion in the study. Participants will also be informed that they are free to withdraw from the study at any time. All participants must sign an IRB/PB-approved consent form indicating their consent to participate. This consent form meets the requirements of the Code of Federal

Regulations and the Institutional Review Board/Privacy Board of this Center. The consent form will include the following:

1. The nature and objectives, potential risks and benefits of the intended study.
2. The length of study and the likely follow-up required.
3. Alternatives to the proposed study. (This will include available standard and investigational therapies. In addition, patients will be offered an option of supportive care for therapeutic studies.)
4. The name of the investigator(s) responsible for the protocol.
5. The right of the participant to accept or refuse study interventions/interactions and to withdraw from participation at any time.

Before any protocol-specific procedures can be carried out, the consenting professional will fully explain the aspects of patient privacy concerning research specific information. In addition to signing the IRB Informed Consent, all patients must agree to the Research Authorization component of the informed consent form.

Each participant and consenting professional will sign the consent form. The participant must receive a copy of the signed informed consent form.

20.1 APPENDICES

Appendix 1: Dosing Modification and Toxicity Management Guidelines for Immune-mediated, Infusion-Related, and Non Immune-mediated Reactions for Durvalumab Monotherapy

Appendix 2: Durvalumab Dose Calculations

APPENDIX 1: Dosing Modification and Toxicity Management Guidelines for Immune-mediated, Infusion-Related, and Non Immune-mediated Reactions related to Durvalumab Monotherapy

Appendix 1 Dosing Modification and Toxicity Management Guidelines for Immune-mediated, Infusion-Related, and Non Immune-mediated Reactions for Durvalumab Monotherapy 1 November 2017 Version

General Considerations	
Dose Modifications	Toxicity Management
Drug administration modifications of study drug/study regimen will be made to manage potential immune-related AEs based on severity of treatment-emergent toxicities graded per NCI CTCAE v4.03. In addition to the criteria for permanent discontinuation of study drug/study regimen based on CTC grade/severity (table below), permanently discontinue study drug/study regimen for the following conditions: 
• Inability to reduce corticosteroid to a dose of ≤ 10 mg of prednisone per day (or equivalent) within 12 weeks after last dose of study drug/study regimen• Recurrence of a previously experienced Grade 3 treatment-related AE following resumption of dosing	It is recommended that management of immune-mediated adverse events (imAEs) follows the guidelines presented in this table: 
– It is possible that events with an inflammatory or immune mediated mechanism could occur in nearly all organs, some of them not noted specifically in these guidelines.– Whether specific immune-mediated events (and/or laboratory indicators of such events) are noted in these guidelines or not, patients should be thoroughly evaluated to rule out any alternative etiology (e.g., disease progression, concomitant medications, and infections) to a possible immune-mediated event. In the absence of a clear alternative etiology, all such events should be managed as if they were immune related. General recommendations follow.– Symptomatic and topical therapy should be considered for low-grade (Grade 1 or 2, unless otherwise specified) events.– For persistent (>3 to 5 days) low-grade (Grade 2) or severe (Grade ≥ 3) events, promptly start prednisone 1 to 2 mg/kg/day PO or IV equivalent.– Some events with high likelihood for morbidity and/or mortality – e.g., myo-carditis, or other similar events even if they are not currently noted in the guidelines – should progress rapidly to high dose IV corticosteroids (methylprednisolone at 2 to 4 mg/kg/day) even if the event is Grade 2, and if clinical suspicion is high and/or there has been clinical confirmation. Consider, as necessary, discussing with the study physician, and promptly pursue specialist consultation.– If symptoms recur or worsen during corticosteroid tapering (28 days of taper), increase the corticosteroid dose (prednisone dose [e.g., up to 2 to 4 mg/kg/day PO or IV equivalent]) until stabilization or improvement of symptoms, then resume corticosteroid tapering at a slower rate (>28 days of taper).– More potent immunosuppressives such as TNF inhibitors (e.g., infliximab) (also refer to the individual sections of the imAEs for specific type of immunosuppressive) should be considered for events not responding to systemic steroids. Progression to use of more potent immunosuppressives should proceed more rapidly in events with high likelihood for morbidity and/or mortality – e.g., myocarditis, or other similar events even if they are not currently noted in the guidelines – when these events are not responding to systemic steroids.– With long-term steroid and other immunosuppressive use, consider need for Pneumocystis jirovecii pneumonia (PJP),
Grade 1 No dose modification	
Grade 2 Hold study drug/study regimen dose until Grade 2 resolution to Grade ≤ 1 . If toxicity worsens, then treat as Grade 3 or Grade 4. Study drug/study regimen can be resumed once event stabilizes to Grade ≤ 1 after completion of steroid taper. Patients with endocrinopathies who may require prolonged or continued steroid replacement can be retreated with study drug/study regimen on the following conditions: 
1. The event stabilizes and is controlled.2. The patient is clinically stable as per Investigator or treating physician's clinical judgement.3. Doses of prednisone are at ≤ 10 mg/day or equivalent.	
Grade 3 Depending on the individual toxicity, study drug/study regimen may be permanently discontinued. Please refer to guidelines below.	
Grade 4 Permanently discontinue study drug/study regimen.	

Appendix 1 Dosing Modification and Toxicity Management Guidelines for Immune-mediated, Infusion-Related, and Non Immune-mediated Reactions for Durvalumab Monotherapy 1 November 2017 Version

General Considerations

Dose Modifications	Toxicity Management

Note: For Grade ≥ 3 asymptomatic amylase or lipase levels, hold study drug/study regimen, and if complete work up shows no evidence of pancreatitis, study drug/study regimen may be continued or resumed.
 
Note: Study drug/study regimen should be permanently discontinued in Grade 3 events with high likelihood for morbidity and/or mortality – e.g., myocarditis, or other similar events even if they are not currently noted in the guidelines. Similarly, consider whether study drug/study regimen should be permanently discontinued in Grade 2 events with high likelihood for morbidity and/or mortality – e.g., myocarditis, or other similar events even if they are not currently noted in the guidelines – when they do not rapidly improve to Grade <1 upon treatment with systemic steroids and following full taper
 
Note: There are some exceptions to permanent discontinuation of study drug for Grade 4 events (i.e., hyperthyroidism, hypothyroidism, Type 1 diabetes mellitus).
	
formerly known as Pneumocystis carinii pneumonia) prophylaxis, gastrointestinal protection, and glucose monitoring.
 
– Discontinuation of study drug/study regimen is not mandated for Grade 3/Grade 4 inflammatory reactions attributed to local tumor response (e.g., inflammatory reaction at sites of metastatic disease and lymph nodes). Continuation of study drug/study regimen in this situation should be based upon a benefit-risk analysis for that patient.

AE Adverse event; CTC Common Toxicity Criteria; CTCAE Common Terminology Criteria for Adverse Events; imAE immune-mediated adverse event; IV intravenous; NCI National Cancer Institute; PO By mouth.

Pediatric Considerations

Dose Modifications	Toxicity Management

The criteria for permanent discontinuation of study drug/study regimen based on CTC grade/severity is the same for pediatric patients as it is for adult patients, as well as to permanently discontinue study drug/study regimen if unable to reduce corticosteroid \leq a dose equivalent to that required for corticosteroid replacement therapy within 12 weeks after last dose of study drug/study regimen
	
– All recommendations for specialist consultation should occur with a pediatric specialist in the specialty recommended.– The recommendations for dosing of steroids (i.e., mg/kg/day) and for IV IG and plasmapheresis that are provided for adult patients should also be used for pediatric patients.– The infliximab 5 mg/kg IV dose recommended for adults is the same as recommended for pediatric patients ≥ 6 years old. For dosing in children younger than 6 years old, consult with a pediatric specialist.– For pediatric dosing of mycophenolate mofetil, consult with a pediatric specialist.– With long-term steroid and other immunosuppressive use, consider need for PJP prophylaxis, gastrointestinal protection, and glucose monitoring.

Specific Immune-Mediated Reactions

Adverse Events	Severity Grade of the Event (NCI CTCAE version 4.03)	Dose Modifications	Toxicity Management
Pneumonitis/Interstitial Lung Disease (ILD)	Any Grade	General Guidance	For Any Grade:
			
 – Monitor patients for signs and symptoms of pneumonitis or ILD (new onset or worsening shortness of breath or cough). Patients should be evaluated with imaging and pulmonary function tests, including other diagnostic procedures as described below. – Initial work-up may include clinical evaluation, monitoring of oxygenation via pulse oximetry (resting and exertion), laboratory work-up, and high-resolution CT scan.
	Grade 1 (asymptomatic, clinical or diagnostic observations only; intervention not indicated)	No dose modifications required. However, consider holding study drug/study regimen dose as clinically appropriate and during diagnostic work-up for other etiologies.	For Grade 1 (radiographic changes only): 
 – Monitor and closely follow up in 2 to 4 days for clinical symptoms, pulse oximetry (resting and exertion), and laboratory work-up and then as clinically indicated. – Consider Pulmonary and Infectious disease consult.
	Grade 2 (symptomatic; medical intervention indicated; limiting instrumental ADL)	Hold study drug/study regimen dose until Grade 2 resolution to Grade ≤ 1 . 
 • If toxicity worsens, then treat as Grade 3 or Grade 4. • If toxicity improves to Grade ≤ 1, then the decision to reinitiate study drug/study regimen will be based upon treating physician's clinical judgment and after completion of steroid taper. 	For Grade 2 (mild to moderate new symptoms): 
 – Monitor symptoms daily and consider hospitalization. – Promptly start systemic steroids (e.g., prednisone 1 to 2 mg/kg/day PO or IV equivalent). – Reimage as clinically indicated. – If no improvement within 3 to 5 days, additional workup should be considered and prompt treatment with IV methylprednisolone 2 to 4 mg/kg/day started – If still no improvement within 3 to 5 days despite IV methylprednisolone at 2 to 4 mg/kg/day, promptly start immunosuppressive therapy such as TNF inhibitors (e.g., infliximab at 5 mg/kg every 2 weeks). Caution: It is important to rule out sepsis and refer to infliximab label for general guidance before using infliximab. – Once the patient is improving, gradually taper steroids over ≥ 28 days and consider prophylactic antibiotics, antifungals, or anti-PJP treatment (refer to current NCCN guidelines for treatment of cancer-related infections [Category 2B recommendation])^a – Consider pulmonary and infectious disease consult.

		
 Consider, as necessary, discussing with study physician.
Grade 3 or 4 (Grade 3: severe symptoms; limiting self-care ADL; oxygen indicated)	Permanently discontinue study drug/study regimen.	For Grade 3 or 4 (severe or new symptoms, new/worsening hypoxia, life-threatening): 
 Promptly initiate empiric IV methylprednisolone 1 to 4 mg/kg/day or equivalent. Obtain Pulmonary and Infectious disease consult; consider, as necessary, discussing with study physician. Hospitalize the patient. Supportive care (e.g., oxygen). If no improvement within 3 to 5 days, additional workup should be considered and prompt treatment with additional immunosuppressive therapy such as TNF inhibitors (e.g., infliximab at 5 mg/kg every 2 weeks' dose) started. Caution: rule out sepsis and refer to infliximab label for general guidance before using infliximab. Once the patient is improving, gradually taper steroids over \geq28 days and consider prophylactic antibiotics, antifungals, and, in particular, anti-PJP treatment (refer to current NCCN guidelines for treatment of cancer-related infections [Category 2B recommendation]).^a
Diarrhea/Colitis	Any Grade	General Guidance
		For Any Grade: 
 Monitor for symptoms that may be related to diarrhea/enterocolitis (abdominal pain, cramping, or changes in bowel habits such as increased frequency over baseline or blood in stool) or related to bowel perforation (such as sepsis, peritoneal signs, and ileus). Patients should be thoroughly evaluated to rule out any alternative etiology (e.g., disease progression, other medications, or infections), including testing for clostridium difficile toxin, etc. Steroids should be considered in the absence of clear alternative etiology, even for low-grade events, in order to prevent potential progression to higher grade event. Use analgesics carefully; they can mask symptoms of perforation and peritonitis.
Grade 1 (Diarrhea: stool frequency of <4 over baseline per day) (Colitis: asymptomatic; clinical or	No dose modifications.	For Grade 1: 
 Monitor closely for worsening symptoms. Consider symptomatic treatment, including hydration, electrolyte replacement, dietary changes (e.g., American Dietetic Association colitis diet), and loperamide. Use probiotics as per treating physician's clinical judgment.

diagnostic observations only)

Grade 2

(Diarrhea: stool frequency of 4 to 6 over baseline per day) (Colitis: abdominal pain; mucus or blood in stool)

Hold study drug/study regimen

until resolution to Grade ≤ 1

- If toxicity worsens, then treat as Grade 3 or Grade 4.
- If toxicity improves to Grade ≤ 1 , then study drug/study regimen can be resumed after completion of steroid taper.

Grade 3 or 4

(Grade 3 diarrhea: stool frequency of ≥ 7 over baseline per day; Grade 4 diarrhea: life threatening consequences)

(Grade 3 colitis: severe abdominal pain, change in bowel habits, medical intervention indicated, peritoneal signs; Grade 4 colitis: life-threatening

Grade 3

Permanently discontinue study drug/study regimen for Grade 3 if toxicity does not improve to Grade ≤ 1 within 14 days; study drug/study regimen can be resumed after completion of steroid taper.

Grade 4

Permanently discontinue study drug/study regimen.

consequences, urgent intervention indicated)	infections [Category 2B recommendation]). ^a
Hepatitis (elevated LFTs) Infliximab should not be used for management of immune-related hepatitis.	Any Grade General Guidance For Any Grade: 
 Monitor and evaluate liver function test: AST, ALT, ALP, and TB. Evaluate for alternative etiologies (e.g., viral hepatitis, disease progression, concomitant medications).
PLEASE SEE shaded area immediately below this section to find guidance for management of “Hepatitis (elevated LFTs)” in HCC patients	Grade 1 $(\text{AST or ALT} > \text{ULN and} \leq 3.0 \times \text{ULN and/or} \text{TB} > \text{ULN and} \leq 1.5 \times \text{ULN})$ 
 No dose modifications. If it worsens, then treat as Grade 2 event. For Grade 1: 
 Continue LFT monitoring per protocol. Grade 2 $(\text{AST or} \text{ALT} > 3.0 \times \text{ULN and} \leq 5.0 \times \text{ULN and/or} \text{TB} > 1.5 \times \text{ULN and} \leq 3.0 \times \text{ULN})$ 
 Hold study drug/study regimen dose until Grade 2 resolution to Grade ≤ 1. If toxicity worsens, then treat as Grade 3 or Grade 4. If toxicity improves to Grade ≤ 1 or baseline, resume study drug/study regimen after completion of steroid taper. For Grade 2: 
 Regular and frequent checking of LFTs (e.g., every 1 to 2 days) until elevations of these are improving or resolved. If no resolution to Grade ≤ 1 in 1 to 2 days, consider, as necessary, discussing with study physician. If event is persistent (> 3 to 5 days) or worsens, promptly start prednisone 1 to 2 mg/kg/day PO or IV equivalent. If still no improvement within 3 to 5 days despite 1 to 2 mg/kg/day of prednisone PO or IV equivalent, consider additional work up and start prompt treatment with IV methylprednisolone 2 to 4 mg/kg/day. If still no improvement within 3 to 5 days despite 2 to 4 mg/kg/day of IV methylprednisolone, promptly start immunosuppressives (i.e., mycophenolate mofetil).^a Discuss with study physician if mycophenolate mofetil is not available. Infliximab should NOT be used. Once the patient is improving, gradually taper steroids over ≥ 28 days and consider prophylactic antibiotics, antifungals, and anti-PJP treatment (refer to current NCCN guidelines for treatment of cancer-related infections [Category 2B recommendation]).^a Grade 3 or 4 $(\text{Grade 3: AST or} \text{ALT} > 5.0 \times \text{ULN and} \leq 20.0 \times \text{ULN and/or} \text{TB} > 3.0 \times \text{ULN and} \leq 10.0 \times \text{ULN})$ For Grade 3: 
 For elevations in transaminases $\leq 8 \times \text{ULN}$, or elevations in bilirubin $\leq 5 \times \text{ULN}$: Hold study drug/study regimen dose until resolution to Grade ≤ 1 or baseline For Grade 3 or 4: 
 Promptly initiate empiric IV methylprednisolone at 1 to 4 mg/kg/day or equivalent. If still no improvement within 3 to 5 days despite 1 to 4 mg/kg/day methylprednisolone IV or equivalent, promptly start treatment with immunosuppressive therapy (i.e.,
